2.2 Secondary Goals

- 2.21 Assess the safety and tolerability of futibatinib and pembrolizumab combination through adverse event monitoring.
- 2.22 Determine the overall objective response rate (ORR) and overall survival (OS) of patients with advanced HCC treated with futibatinib and pembrolizumab combination.
- 2.23 Assess change in overall health-related quality of life, as measured by the global health domain of the European Organization for Research and Treatment of Cancer Quality of Life Questionnaire (EORTC-QLQ-C30) between baseline and at time of first-restaging scan.

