8.2 Dose Modifications for Futibatinib

8.21 Dose Modifications for Futibatinib for Expected Adverse Events

CTCAE System/Organ/Class (SOC)	ADVERSE EVENT	ACTION**
Blood and lymphatic system disorders	Anemia Grade 3	Omit dose until resolved to \leq Grade 1 or baseline • If resolved \leq 7 days, then maintain dose level • If resolved $>$ 7 days, then reduce 1 dose level
	Grade 4	Omit dose until resolved to \leq Grade 1 or baseline
Blood and lymphatic system disorders	Febrile neutropenia	Omit dose until resolved, then reduce 1 dose level
Eye disorders	Eye disorders - Other, specify - retinal pigment epithelial detachment (RPED)	Continue at current dose and continue periodic ophthalmic evaluation: • If resolved \leq 14 days to \leq Grade 1, then maintain dose level • If resolved $>$ 14 days to \leq Grade 1, then omit dose until resolved, then resume at same dose level or a lower dose
Gastrointestinal disorders	Diarrhea Grade 2	Omit futibatinib dose until resolved to \leq Grade 1 or baseline
	Grade 3	Omit dose until further evaluation and cause is determined If resolved within 21 days, and deemed related to futibatinib, then reduce 1 dose level
Gastrointestinal disorders	Mucositis oral Grade 3	If AE persists despite optimal supportive care: Omit futibatinib dose until resolved to \leq Grade 1 or baseline
Gastrointestinal disorders	Nausea Grade 3	If AE persists despite optimal supportive care (See Section 9.0): Omit futibatinib dose until resolved to \leq Grade 1 or baseline
Gastrointestinal disorders	Vomiting Grade 3	If AE persists despite optimal supportive care (See Section 9.0): Omit futibatinib dose until resolved to \leq Grade 1 or baseline
Investigations	Alanine aminotransferase increased >5 x ULN AND Aspartate aminotransferase increased >5 x ULN AND Blood bilirubin increased ≥ 3 x ULN	Omit futibatinib for up to 14 days until resolved to \leq Grade 1 or baseline, then restart at same dose level If related to futibatinib then reduce 1 dose level
Investigations	For ALT >20 x ULN, and AST >20 x ULN, or Blood bilirubin increased >10 x ULN	Permanently discontinue futibatinib

CTCAE System/Organ/Class (SOC)	ADVERSE EVENT	ACTION**

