Investigations	Hyperphosphatemia Grade 3 Serum phosphorus level >7 - ≤10 mg/dL	Dose reduce futibatinib to the next lower dose level and initiate or intensify phosphate lowering therapy (See Section 9.0 for management suggestions) Re-assess serum phosphate within 7 days and at least once a week. If the serum phosphorus level has resolved to ≤Grade 2 within 14 days after dose reduction, continue futibatinib at the reduced dose level. If the serum phosphorus level has not resolved to ≤Grade 2 after 14 days, further reduce futibatinib from the last reduced dose level (or no lower than 12 mg QD). If the serum phosphorus level has not resolved to ≤Grade 2 after 14 days of the second dose reduction of futibatinib (or no lower than 12 mg QD), omit dosing with futibatinib until it is resolved to ≤Grade 2 before resuming futibatinib at the reduced dose prior to dose interruption.
Investigations	Hyperphosphatemia Grade 4 Serum phosphate >10 mg/dL	Omit futibatinib until it is resolved to ≤Grade 2, then resume futibatinib at the next lower dose level and intensify phosphate lowering therapy Re-assess serum phosphate within 7 days and at least once a week If after 2 dose interruptions and 2 dose reductions the serum phosphorus level has not resolved to ≤Grade 2 after 14 days, permanently discontinue futibatinib
Investigations	Neutrophil count decreased Grade 4	Omit dose until resolved to ≤Grade 2 or baseline • If resolved ≤7 days, then maintain dose level • If resolved >7 days, then reduce 1 dose level
Investigations	Platelet count decreased Grade 3	Omit dose until resolved to ≤Grade 1 or baseline • If resolved ≤7 days, then maintain dose level • If resolved >7 days, then reduce 1 dose level
	Grade 4	Omit dose until resolved to ≤Grade 1 or baseline, then reduce 1 dose level
Skin and subcutaneous tissue disorders	Palmar-plantar erythrodysesthesia syndrome Grade 3	Omit dose until resolved to ≤Grade 1 or baseline • If resolved ≤21 days, then maintain dose level • If resolved >21 days, then reduce 1 dose level
	Rash, maculopapular	Omit dose until resolved to ≤Grade 1 or baseline • If resolved ≤21 days, then maintain dose level • If resolved >21 days, then reduce 1 dose level
All others not specified above and at least possibly related to futibatinib	Grade 3	Omit dose until resolved to ≤Grade 1 or baseline Reduce by 1 dose level from the previous level
	Grade 4 (nonlab)	Discontinue futibatinib

CTCAE System/Organ/Class (SOC)	ADVERSE EVENT	ACTION**

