	Grade 4 lab abnormalities	Omit dose until resolved to \leq Grade 1 or baseline Futibatinib will be permanently discontinued if assessed by the Investigator as life threatening. If it is in the best interest of the patient to continue treatment in the opinion of the Investigator and after discussion with the Sponsor, the patient can continue treatment at a reduced dose level

** Use the following to describe actions in the Action column:

- **Omit** = The current dose(s) for the specified drug(s) during a cycle is skipped. The patient does not make up the omitted dose(s) at a later time.
- **Hold/Delay** = The current dose(s) of all drugs during a cycle is delayed. The patient does make up the delayed dose(s) when the patient meets the protocol criteria to restart drugs.
- **Discontinue** = The specified drug(s) are totally stopped.

NOTE: Interrupt futibatinib if any adverse events are intolerable, regardless of the grade (including Grade 1 and 2). If or when the adverse event resolves to a tolerable state, consideration can be given to resuming futibatinib at the same dose if deemed appropriate or reduced by one dose level if needed

NOTE: If the patient experiences a significant adverse event requiring a dose reduction at the start of the next cycle, then the dose will remain lowered for that entire subsequent cycle. If that cycle is completed with no further adverse events $>$ Grade 2, then the dose may be increased, at the investigator's discretion, one level at a time, in the following cycles.

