10.6 Required Routine Reporting

10.61 Baseline and Adverse Events Evaluations

Pretreatment symptoms/conditions to be graded at baseline and adverse events to be graded at each evaluation.

Grading is per CTCAE v5.0 **unless** alternate grading is indicated in the table below:

CTCAE System/Organ/Class (SOC)	Adverse event/Symptoms	Baseline	Each evaluation
Eye disorders	Dry eye	X	X
	Blurred vision	X	X
	Eye disorders – Other, specify (retinal pigment epithelial detachment RPED)	X	X
Gastrointestinal disorders	# of stools at baseline	X	
	Diarrhea		X
	Mucositis oral	X	X
General disorders and administration site conditions	Fatigue	X	X
Investigations	Alanine aminotransferase increased (ALT)	X	X
	Aspartate aminotransferase increased (AST)	X	X
	Blood bilirubin increased	X	X
	Hyperphosphatemia	X	X

CTCAE System/Organ/Class (SOC)	Adverse event/Symptoms	Baseline	Each evaluation
Skin and subcutaneous tissue disorders	Nail changes	X	X
	Palmar-plantar erythrodysesthesia syndrome	X	X
	Rash maculopapular	X	X

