10.62 All other AEs

Submit via appropriate MCCC Case Report Forms (i.e., paper or electronic, as applicable) the following AEs experienced by a patient and not specified in Section 10.6:

10.621 Grade 2 AEs deemed *possibly, probably, or definitely* related to the study treatment or procedure.

10.622 Grade 3 and 4 AEs regardless of attribution to the study treatment or procedure.

10.623 Grade 5 AEs (Deaths)

10.6231 Any death within 30 days of the patient's last study treatment or procedure regardless of attribution to the study treatment or procedure.

10.6232 Any death more than 30 days after the patient's last study treatment or procedure that is felt to be at least possibly treatment related must also be submitted as a Grade 5 AE, with a CTCAE type and attribution assigned.

10.624 Outcome of Adverse Events

Record the outcome of AEs as follows:

- Resolved
- Not resolved/ Ongoing
- Fatal/ Death

10.625 Follow-up of Adverse Events

Any ongoing AEs should be followed until the earliest occurrence of one of the following:

- The AE has resolved or stabilized
- Completion of safety follow-up visit
- Start of new antitumor therapy
- Withdrawal of consent
- Death
- Other (eg, transfer to another hospital)

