16.2 Secondary Endpoints

Secondary endpoints include: overall response rate (ORR), overall survival (OS), incidence of adverse events, and quality of life.

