16.6.3 Incidence of Adverse Events (AEs)

Adverse events will be evaluated, per CTCAE v5.0, for each patient. Grade 3+ AEs, at least possibly related, which occur more than 10% of patients will be reported by grade.

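### Section 16.6.3 commits only to related Grade 3+ adverse events in more than 10% of patients, so Grade 1-2 toxicity, and related Grade 3-5 events in one or two patients, have no planned summary

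*Combined protocol and SAP*

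**What the plan says.** Goal 2.21 reads: "Assess the safety and tolerability of futibatinib and pembrolizumab combination through adverse event monitoring". Section 16.2 sets no grade limit on the matching endpoint: "Secondary endpoints include: overall response rate (ORR), overall survival (OS), incidence of adverse events, and quality of life".

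Section 16.6.3 has two sentences. The first says that adverse events will be evaluated in each patient by CTCAE v5.0. It names no grade range, statistic or table. The second is the output rule: "Grade 3+ AEs, at least possibly related, which occur more than 10% of patients will be reported by grade".

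Collection is wider than that output. Section 10.61 requires: "Pretreatment symptoms/conditions to be graded at baseline and adverse events to be graded at each evaluation". Its list sets no minimum grade. Section 10.62 then covers "the following AEs experienced by a patient and not specified in Section 10.6", namely related Grade 2 events, Grade 3 and 4 events whatever their attribution, and deaths.

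Dosing also responds to low grades. In Section 8.21 the row "Diarrhea Grade 2" leads to omission of futibatinib until recovery, and a note after the table says: "Interrupt futibatinib if any adverse events are intolerable, regardless of the grade (including Grade 1 and 2". The row "Rash, maculopapular" also omits the dose, but it shows no grade in the text available, so nothing here rests on it.

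**The concern.** An event must pass three filters to reach the only output that 16.6.3 commits to: Grade 3 or higher, at least possibly related, and present in more than 10% of patients. The neighbouring secondary endpoints each name an estimate: ORR with a binomial interval, OS by Kaplan-Meier, and quality of life by Hodges-Lehmann. Adverse event incidence has only this filtered list.

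Two groups of events drop out. The first is all Grade 1-2 toxicity, including events that the protocol itself treats as reason to stop a daily oral drug. The second is uncommon related severe events, up to and including Grade 5, when only one or two patients have them. Section 7.5 says that the two agents' safety had been evaluated individually and that the run-in is there to ensure the safety of the combination. A description of how the combination was tolerated is therefore one of the main things this trial can supply. If the table is not planned, the choice of which low-grade toxicities to show is left until the data are known.

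**Working it through.** **Inputs.** The output rule is from 16.6.3, the 22 evaluable and 25 maximum patients from 16.3, the FGF19-positive analysis population from 16.6, and the graded terms from 10.61. I read the 10% as applying to each adverse event term. Section 16.6.3 does not state its denominator, so I use 22 and check 25.

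**The plan's own figures.** Section 16.6.3 prints no count to reproduce. The denominator of 22 fits the design. With complete data, the logit-transformed 80% lower bound is 0.245 at 8/22 and 0.284 at 9/22, so success needs 9. Exact binomial power at 47% is then 0.783, ignoring the interim look, against 80% in 16.3 and 0.7923 in 16.5. Nothing below depends on the power.

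**Step 1, threshold.** The smallest count above 10% is floor(0.10 × n) + 1.
- n = 22: 0.10 × 22 = 2.2, so 3 patients (3/22 = 13.6%).
- n = 25: 0.10 × 25 = 2.5, so 3 patients (3/25 = 12%).

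**Step 2, terms in 10.61.** The table has 14 rows. The stool count is taken at baseline only, which leaves 13 terms graded at each evaluation: dry eye, blurred vision, retinal pigment epithelial detachment, diarrhea, oral mucositis, fatigue, ALT, AST, bilirubin, hyperphosphatemia, nail changes, palmar-plantar erythrodysesthesia and maculopapular rash. Twelve have a baseline grade; diarrhea has the stool count instead.

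**Step 3, what the rule keeps at n = 22.**

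| Observed for one term | In the committed summary? |
|---|---|
| Grade 1-2, any number up to 22/22 | No |
| Related Grade 3-5 in 1/22 (4.5%) | No |
| Related Grade 3-5 in 2/22 (9.1%) | No |
| Related Grade 3-5 in 3/22 (13.6%) | Yes |

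**Step 4, what 2 of 22 is compatible with.** The Clopper-Pearson 95% limits are the 2.5% point of Beta(x, n − x + 1) and the 97.5% point of Beta(x + 1, n − x). With x = 2 and n = 22, Beta(2, 21) gives 0.011 and Beta(3, 20) gives 0.292, that is 1.1% to 29.2%. The largest count that the rule hides is thus compatible with a true rate well above 10%.

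**Step 5, chance that a related Grade 3+ term is not shown.** P(X ≤ 2) = Σ C(22, k) p^k (1 − p)^(22 − k) for k = 0, 1, 2. At p = 0.10 this is 0.098 + 0.241 + 0.281 = 0.620.

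| Assumed true rate | n = 22 | n = 25 |
|---|---|---|
| 10% | 62% | 54% |
| 15% | 34% | 25% |
| 20% | 15% | 10% |

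These rates are my assumptions. The documents give no rates by grade for the combination.

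**The case against.** The strongest reply is that 16.6.3 is only terse. Its heading and first sentence cover all adverse events, the second sentence does not contain the word only, and a team could produce an all-grade table at any time from data that 10.61 already requires. That stands as far as it goes: a wider summary is permitted and no data are lost. But permission is not a plan, and the one output rule that is written would satisfy the section while leaving these events out.

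It is also fair that no decision depends on Grade 1-2 incidence, and that a display threshold is a choice about reporting, not a bias. Low-grade events are managed through the dose rules and seen in the monthly and DSMB reviews. This limits the harm, but none of it is a final estimate.

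A reader might infer three stronger things that the documents do not support.
- That low-grade toxicity goes uncollected, or that reporting it is ruled out. Sections 10.61 and 10.62 collect it, and nothing forbids reporting it.
- That severe events or deaths could escape notice. The run-in rule (7.5), expedited reporting (10.4 and 10.52), the reviews in 16.71 and the stopping rule in 16.72 all work independently of 16.6.3.
- That low-grade events cause most dose interruptions. The documents give no such share, and none is claimed here.

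**Conclusion.** The point holds as a gap in planned reporting. Followed literally, 16.6.3 yields no summary of Grade 1-2 toxicity, and none of a related Grade 3-5 event in fewer than 3 patients. Goal 2.21 and the adverse event endpoint in 16.2 are then only partly answered.

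The threshold of 3 patients and the count of 13 terms follow directly from the text. They rest on reading the 10% per term with 22 or 25 as denominator. The probabilities of non-display depend on assumed rates and only show scale. Data collection, the PFS6 analysis, the rule for declaring the regimen promising in 16.4 and safety monitoring are untouched. This is a cheap improvement worth making, not a flaw in the design.

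**What to change.** Make two changes to 16.6.3.
1. Drop the 10% threshold, so that all at-least-possibly-related Grade 3+ events are reported by grade.
2. Add one descriptive table of the 13 terms in 10.61 by maximum on-treatment grade. For each term give the number and percentage of patients newly affected or worse than at baseline, using the baseline stool count for diarrhea. State the denominator.

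Exact confidence intervals are optional. A count of patients with futibatinib interrupted, reduced or discontinued can be added if the case report forms capture it. The forms and the medication diary are not in the documents, so this should be confirmed first. Related Grade 2 events outside the 13 terms would still have no table; a short listing from the 10.62 data would cover them.

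The cost is SAP wording and one longer table, with no new visits, tests or patients. At n = 22 the estimates are imprecise (3/22 is 13.6%, exact 95% CI 2.9% to 34.9%), so the table should be labelled descriptive and carry no test.

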16.6.4 Quality of Life (QoL) Outcomes

To assess overall health-related quality of life, as measured by the global health domain of the European Organization for Research and Treatment of Cancer Quality of Life Questionnaire (EORTC-QLQ-C30). The raw score will be calculated per scoring manual³⁰ and transformed to scores ranging from 0 to 100. Change in score between baseline and first re-staging will be calculated for each individual. The median QOL change from baseline along with a 95% CI will be estimated using the Hodges-Lehmann method.³¹

16.6.5 Prognostic effect of baseline cfDNA

Cox proportional hazard model will be used to evaluate the prognostic effect of baseline cfDNA.

16.67 Correlation of drug response in patient derived organoid with clinical response
The correlation of drug response in patient derived organoid with clinical response will be tested using Chi-square test.

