¹¹ Every 2 months for first 6 months and every 3 months until 3 months after last dose of futibatinib; Order at any time if clinically indicated.

¹² Every 3 months until 3 months after last dose of futibatinib; Order at any time if clinically indicated

¹³ Nutrition consult may be done one time at anytime after starting treatment as needed. (This exam is part of expanded patient care.)

¹⁴ Testing may be done on archived tissue at any time after registration – not required to be prior to C1D1 (see [Section 17.0](#))

¹⁵ Performed in all HCC patients at baseline

Tests and procedures ¹	Screening ≤21 days prior to registration	Active Monitoring Phase							Obs Clinical follow-up ⁴
		After Reg prior to C1D1 Tx	Cycle 1 Days 8, 15	End of every cycle	End of every 3 cycles (Cycles 1-9) ²	End of every 2 cycles (Cycles 10+) ³	End of treatment	Safety follow-up: 30 days post treatment	
Clinical tumor genomic testing ¹⁶		X							
Tumor measurement ¹⁷	X ¹⁸				X ¹⁹	X ²⁰	X		X
Tumor biopsy	X ^{21R}								
Research blood specimens ^{22R}		X			X ²³		X		
Research tissue specimens ^{24R}	X						X		
Patient medication diary (Appendix V) ²⁵				X			X		
Patient questionnaire booklets (Appendix VII)		X			X ²⁶		X		

Cycle = 21 days ±3 days for Cycles 1-9; Cycle = 42 days ±7 days for Cycles 10+; R= Research funded (See Section 19.0)

¹⁶ Clinical testing – Note: Molecular analysis including next generation sequencing (NGS) to be done per clinical practice – should be ordered/tested any time prior to end of treatment and results should be uploaded in Medidata Rave® when available

¹⁷ To be performed per Mayo Clinic Cancer Center guidelines – For HCC usually CT chest/abdomen/pelvis or CT chest and MRI abdomen/pelvis; NOTE: If pseudoprogression is suspected at any time, repeat imaging after two more cycles of treatment.

¹⁸ Can be performed ≤28 days prior to registration

¹⁹ To be performed about every 9 weeks (or 3 cycles), ≤7 days prior to planned Day 1 of Cycles 4, and 7 or as clinically indicated

²⁰ To be performed about every 12 weeks, ≤7 days prior to planned Day 1 of Cycles 10, 12, 14 etc., or as clinically indicated

²¹ Research biopsy should be done after registration and prior to treatment on C1D1. Research biopsy may be omitted after discussion with PI, (e.g., if it is not medically feasible, or exceeds lab capacity, or other reason).

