16.3 Sample Size

We plan to accrue 22 evaluable patients. Evaluable patient is defined as those who are eligible, consented, are positive for FGF19, received any protocol treatment, and are without major violation. With 22 evaluable patients, we have 80% power to detect PFS6 from 25% (historical control) to 47%, assuming a 1-sided significance level of 0.1 and an accrual rate of 2 patients per month.

The trial has a single interim analysis for futility and the overall type I error rate is controlled. The interim analysis will be considered non-binding. The accrual will not be halted for the interim analysis.

We anticipate accruing an additional 3 patients to account for ineligibility, cancellation, major treatment violation, or other reasons. Therefore, maximum accrual is projected to be 25 patients. Sample size calculation was based on simulation using R.

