16.6 Analysis Plan for Secondary Outcome and Translational Endpoints

The below analyses will be done on FGF19 positive patients. The analyses will also be performed on FGF19 negative patients as exploratory analyses.

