16.6.1 Objective Response

Objective response by RECIST v1.1 criteria will be estimated using objective response rate (ORR) where ORR is defined as the number of evaluable patients achieving a response (PR or CR per RECIST v1.1) during treatment with study therapy divided by the total number of evaluable patients. Point estimates will be generated for objective response rates along with 95% binomial confidence intervals²⁸.

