17.0 Pathology Considerations/Tissue Biospecimens

17.1 Summary Table of Research Tissue Specimens to be Collected for this Protocol

Research Study (Section for more information)	Specimen Purpose (check all that apply)	Mandatory or Optional	Type of Tissue to Collect	Block, Slides, Core, etc. (# of each to submit)	At any time after Reg*	At time of disease progression	Process at site? (Yes or No)	Temperature Conditions for Storage /Shipping
FGF-19 Testing, and correlative studies including Immunohistochemistry (Section 17.2 and 17.3)	 Eligibility  Correlative	Mandatory	Formalin Fixed Paraffin Embedded	2 cores (or archived 5 unstained slides)*	X		No	Ambient
Patient-derived tumor organoid culture and studies (Section 17.2 and 17.3) Rochester ONLY	 Correlative	Mandatory	Fresh Tissue	4-6 cores or pieces of tissue	X		No	Cold, ice pack
Tumor tissue at disease progression**	 Banking	Optional	Formalin Fixed Paraffin Embedded	3 cores or 10 unstained slides		X	No	Ambient

*All patients should have baseline biopsy for FGF-19 testing and correlative studies. If archived tissue is available and used for FGF-19 testing, then eligible patients will still need a baseline biopsy to collect correlative tissue unless already collected under IRB 17-003174. If baseline biopsy cannot be done (e.g., because not medically feasible or lack of lab capacity), and PI agrees, patient is still eligible if archived tissue is available for FGF-19 screening.

**If biopsy or surgery is done at time of disease progression for clinical reasons, a sample of tumor tissue is requested for comparison with baseline sample

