17.25 Submission/Shipping

- 17.251 Verify that ALL sections of the Tissue Specimen Submission Form (see Forms Packet), BAP Requisition Form (provided in kit), and specimen collection labels are completed and filled in correctly. Enter information from the Tissue Specimen Submission Form into the remote data entry system within 7 days after specimen collection (see Forms Packet).
- 17.252 Rochester ONLY: Fresh tissue specimens collected in tissue media should be placed on cold ice pack (~0°C) and immediately delivered to the following laboratories at Mayo Clinic in Rochester, MN:
[REDACTED]

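### Section 16.67 should name an exact test for organoid versus clinical response, because at the response rates the protocol cites the table is too sparse for a chi-square approximation

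*Combined protocol and SAP*

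**What the plan says.** Section 16.67 is a single sentence: "The correlation of drug response in patient derived organoid with clinical response will be tested using Chi-square test". It mentions no exact test, continuity correction or small-cell rule. It gives no cut-off for organoid response and no definition of clinical response. The only response definition in the statistical section is CR or PR by RECIST v1.1, given for ORR in 16.6.1, and 16.67 does not say that it uses it.

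Three other places limit the number of patients in the table:

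- **Analysis set.** Section 16.6 says "The below analyses will be done on FGF19 positive patients", with FGF19-negative patients analysed separately as exploratory. Section 16.3 says "We plan to accrue 22 evaluable patients", and "maximum accrual is projected to be 25 patients".
- **Site.** The organoid row of the table in 17.1 is marked "Rochester ONLY", and 17.25 repeats the restriction. Section 14.3 gives shipping rules for Arizona and Florida, so other sites are foreseen.
- **Biopsy.** Footnote 21 in section 4.1 says "Research biopsy may be omitted after discussion with PI", with feasibility and laboratory capacity among the reasons.

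The analysis serves objective 2.33, which is exploratory. No alpha, power or decision rule is attached to it.

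**The concern.** The Pearson chi-square p-value is a large-sample approximation, and the usual guide is an expected count of at least 5 in each cell. Here the table has at most 22 patients and responses are expected in a minority, so the approximation is doubtful for the table that will be observed. The organoid result could then be reported as nominally significant on three or four responders, when an exact analysis of the same data would not support that statement. No primary or secondary conclusion depends on it.

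**Working it through.** The plan states no figure for this analysis, so there is nothing to reproduce. The checks assume a 2x2 table.

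**1. Expected counts.** The smallest expected count is (smaller row total x smaller column total) / n. With half the organoids sensitive, the most favourable split, it equals n x 0.5 x response rate. The rates are those the protocol cites for other regimens in HCC: 17% (section 1.2), and 27.3% by RECIST 1.1 and 33.2% by mRECIST (section 1.4).

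| Organoid n | 17% | 27.3% | 33.2% |
|---|---|---|---|
| 22 (all evaluable) | 1.87 | 3.00 | 3.65 |
| 25 (maximum accrual) | 2.12 | 3.41 | 4.15 |
| 12 (assumed) | 1.02 | 1.64 | 1.99 |

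For example, 22 x 0.5 x 0.17 = 1.87. Reaching 5 needs n = 10 / rate, which is 59, 37 or 31 patients, more than maximum accrual in every case. At n = 22, only 5 of the 441 possible margin pairs give 5 or more in every cell, and all need at least 10 responders.

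**2. Example with n = 12 (assumed).** Organoid-sensitive: 3 of 3 responders and 3 of 9 non-responders.

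- Pearson, uncorrected: 12 x (3x6 - 0x3)^2 / (3x9x6x6) = 12 x 324 / 972 = 4.00, p = 0.046.
- With continuity correction: 12 x (18 - 6)^2 / 972 = 1.78, p = 0.182.
- Fisher: the observed table has probability C(6,3)/C(12,3) = 20/220 = 0.0909. The opposite extreme has the same probability, so p = 0.182.
- Mid-p: 2 x 0.0909/2 = 0.091.
- Boschloo: 0.068 to 0.069, depending on which margin is treated as fixed.

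**3. Example with n = 17 (assumed).** Organoid-sensitive: 4 of 4 responders and 5 of 13 non-responders.

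- Pearson: 17 x (4x8)^2 / (4x13x9x8) = 17 x 1024 / 3744 = 4.65, p = 0.031.
- With continuity correction: 17 x (32 - 8.5)^2 / 3744 = 2.51, p = 0.113.
- Fisher: 126/2380 + 70/2380 = 0.0529 + 0.0294 = 0.082.
- Mid-p: 0.0529/2 + 0.0294 = 0.056.
- Boschloo: 0.049 to 0.051.

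**4. Example with n = 22.** Responders: 4 of 11 organoid-sensitive and 0 of 11 resistant patients. Pearson gives 0.027. The observed table has probability C(11,4)/C(22,4) = 330/7315 = 0.0451, so Fisher gives 2 x 0.0451 = 0.090 and mid-p gives 0.045. Here the answer at 0.05 depends on which exact method is used.

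**5. How often the uncorrected test and Fisher disagree.** Consider tables with Pearson p of at most 0.05, 2 to n/2 responders and at least 2 patients in each organoid group. Fisher exceeds 0.05 in 26 of 60 such tables at n = 12 and in 106 of 452 at n = 22. These are counts of tables, not probabilities.

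**6. Average error rate.** Full enumeration under independence, for n from 10 to 22 and a range of response and sensitivity rates, puts the type I error of the uncorrected test at nominal 0.05 between about 0.026 and 0.063.

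**The case against.** The strongest reply is that the planned test does roughly what it promises over repeated use. Step 6 supports this. A reader might infer from the 0.046 against 0.18 pair that the planned p-value is several times too small, or that false positives are inflated several-fold. The documents and the arithmetic do not support that as a general statement:

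- The fourfold gap in the n = 12 example is against Fisher, the most conservative comparator. Against Boschloo or mid-p, the gaps at n = 12 and n = 17 are about 1.5 to 2-fold. Larger Boschloo gaps do occur, but in sparser tables: for 2 of 3 against 1 of 19 responding, Pearson gives 0.0040 and Boschloo 0.030.
- Section 16.67 does not say that the chi-square is uncorrected. A continuity-corrected version (0.182 and 0.113) removes the gap in both of those examples.
- Conditional on the margins, the size of the nominal 5% test can reach 0.18 at n = 12 and 0.20 at n = 15, but these are worst cases. The first needs exactly 3 responders and an even organoid split (or the same with rows and columns exchanged); with 3 responders, every other split gives at most 0.0455. The second needs a margin with a single patient, and otherwise the maximum at n = 15 is 0.095.

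A reader might also infer that expected counts of 5 are out of reach altogether. They are not. If clinical response meant 6-month PFS at the 47% target in 16.3, all 22 patients with an even organoid split would give 22 x 0.5 x 0.47 = 5.17, although 18 patients would give 4.23. Section 16.67 does not adopt that definition, but it does not exclude it either.

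What remains is narrower. On the CR/PR reading, the approximation is unreliable for the observed table, and the plan neither names an alternative nor says which version of the chi-square applies.

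**Conclusion.** The point holds as a cheap improvement to one exploratory analysis. At the cited response rates the smallest expected count is about 1.9 to 3.7 even in the best case of 22 patients and an even organoid split. An uncorrected chi-square can then cross 0.05 where exact tests do not, as in the n = 12 example (0.046 against about 0.07 to 0.18). There is no systematic inflation of the 5% error rate, and the size of the gap varies with the exact method and the continuity correction.

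This rests on a 2x2 table, response defined as CR or PR, and a response rate near those cited for other regimens. The documents state neither the number of patients who will yield organoids nor the fraction that will be sensitive. The 12 and 17 used above are assumptions; the firm limit for the main analysis is 22.

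**What to change.** In section 16.67:

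1. Replace the chi-square test with one exact test named in advance: Fisher's exact, exact mid-p or Boschloo. The choice should not wait for the table, since step 4 shows that the methods can fall on different sides of 0.05.
2. State the cut-off that makes an organoid sensitive, and say whether clinical response means CR or PR by RECIST v1.1 or something else. Neither the test nor the summaries below can be computed without these definitions.
3. Report the sensitivity and specificity of organoid response with exact 95% confidence intervals, in line with the exact binomial intervals already planned for ORR. These show how little a few responders can establish. With 3 of 3 responders organoid-sensitive, the lower limit is 0.025^(1/3) = 0.29, so the interval runs from 29% to 100%.

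The cost is a few lines of SAP text and agreement with the organoid laboratory on a cut-off. The statistical downside is that Fisher's test is somewhat conservative. Mid-p and Boschloo are less so, but mid-p does not strictly guarantee the nominal level.
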